5. STUDY DESIGN

5.1 General Study Design

This is a Phase 1, multi-site, open label, nonrandomized, exploratory study to assess delivery of LMN-201 components via enteric capsules.

The trial will be evaluated through 2 cohorts of up to 6 subjects each. The first cohort will utilize specific components to allow analysis of individual component digestion. Eligible subjects with mature ileostomies will be consented, enrolled, assigned to treatment sequentially, and asked to swallow the following:

Subject	Number of capsules administered to subject—First cohort					
	Anti-toxin B VHH-1	Anti-toxin B VHH-2	Anti-toxin B VHH-3	Lysin capsules	Capsule with tube-shaped transit markers	Capsule with ring-shaped transit markers
1	3	—	—	1	1	1
2	3	—	—	1	1	1
3	—	3	—	1	1	1
4	—	3	—	1	1	1
5	—	—	3	1	1	1
6	—	—	3	1	1	1

Every hour after ingestion, ileostomy fluid will be collected, weighed, filtered, and analyzed for the presence of capsules and/or transit markers. This procedure will be repeated for four hours after the capsules and/or transit marker are observed in the ileostomy collection, or 12 hours after ingestion, whichever time is shorter.

The trial will be adapted between the first and the second cohort in the following manner:

- If intact enteric capsules are observed in the ileostomy fluid of more than one participant
 - And the transit time is less than 4 hours, then a fluid restriction to less than 150 ml per hour will be implemented for the second cohort.
 - And the transit time is greater than 4 hours, then immediate release capsules will be utilized for the second cohort.
- If the number of enteric capsules that remain encapsulated in the ileostomy fluid is less than 20%
 - Then the number of subjects in the second cohort will decrease to three.

The second cohort, allowing for the above changes, will utilize a ‘cocktail’ formulation of VHHS. Subjects will be asked to swallow the following:

Subject	Number of capsules administered to subject—Second cohort					
	Anti-toxin B VHH-1	Anti-toxin B VHH-2	Anti-toxin B VHH-3	Lysin capsules	Capsule with tube-shaped transit markers	Capsule with ring-shaped transit markers
1	1	1	1	1	1	1
2	1	1	1	1	1	1
3	1	1	1	1	1	1

Any changes not described above will only be implemented once a protocol amendment has been submitted to the appropriate Institutional Review Board (IRB) or Independent Ethics Committee (IEC), and has been reviewed and approved.

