1. PROTOCOL SUMMARY

1.1 Synopsis

Study Title: Exploratory study to assess delivery of LMN-201 components via enteric capsules in the gut of individuals with ileostomies	
Study Number: CDI01	
Phase of development: Phase 1	
Investigational Product: Components of LMN-201 (a cocktail consisting of a bacteriophage lysin specific for C. difficile organism and three VHH-derived proteins that bind and inhibit C. difficile toxin B, delivered in whole, spray-dried spirulina (Arthrospira platensis) biomass)	
Sponsor: Lumen Bioscience, Inc.	
Principal Investigator (PI): [name]	
Study Center: Coral Sea Clinical Research Institute	
Study Objectives (Primary):	
 To determine if enteric capsules are sufficient to deliver LMN-201 therapeutic proteins (VHH proteins and lysin) to the terminal ileum.
Study Objectives (Exploratory):	
 To document the presence of LMN-201 therapeutic proteins at the terminal ileum To determine variability between individuals in the quantity of LMN-201 therapeutic proteins at the terminal ileum
Subject Population	Adults aged 19 and above with mature ileostomy
Study Design	
This is a Phase 1, multi-site, open label, exploratory study of LMN-201 to evaluate the function of enteric capsules on drug release.
 
Eligible volunteers with mature ileostomies will be enrolled and sequentially assigned to treatment. After documentation of informed consent, subjects will be asked to swallow 4 enteric capsules of LMN-201 components, 1 enteric capsule containing ring-shaped transit markers, and 1 immediate release capsule containing tube-shaped transit markers. Every hour following ingestion, ileostomy fluid will be collected, weighed, filtered, and analyzed. The procedure will be repeated for 4 hours after capsules and/or transit markers are observed in the collected ileostomy fluid, or 12 hours after ingestion, whichever time is shorter.
 
In the first cohort, participants will receive only one of the LMN-201 VHH proteins administered in 3 enteric capsules as well as 1 enteric capsule containing lysin, 1 enteric capsule containing ring-shaped transit markers, and 1 immediate release capsule containing tube-shaped transit markers. In the second cohort, participants will receive 1 enteric capsule of each of the LMN-201 VHH proteins as well as 1 enteric capsule containing lysin, 1 enteric

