5.4 End of Study Definition

Each subject will complete the study in a single calendar day. Each cohort will be considered completed when the total number of participants have completed their participation. The study will be considered completed when both cohorts have completed their participation and the data has been delivered and approved.

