7.4 Early Termination

Subjects have the right to withdraw from the study at any time and for any reason. Subjects who withdraw their consent will not receive any further study drug but will be offered all follow-up safety assessments.

Subjects who withdraw from the study prior to treatment will be replaced per recruitment and enrollment processes outlined above in 6.3.

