11.2 Sample Size Considerations

No statistical hypothesis is required to be tested. Therefore, no formal sample size calculations have been made. The sample size has been determined to be up to six (6) per cohort to provide preliminary information.

Overall, up to 12 human subjects will be exposed to the IP.

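### Cohort 1 assigns the three VHHs in consecutive pairs, so a cohort that ends at three or four subjects has no single-VHH data on VHH-3; an interleaved order would cover all three at the same totals

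*Protocol*

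**What the plan says.** Protocol section 5.1 describes an open-label, nonrandomized study and sets its size: "The trial will be evaluated through 2 cohorts of up to 6 subjects each". Section 11.2 repeats this as a maximum, with no hypothesis test behind it: "The sample size has been determined to be up to six (6) per cohort to provide preliminary information".

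The purpose of cohort 1 is given in section 5.1: "The first cohort will utilize specific components to allow analysis of individual component digestion". Eligible subjects are "assigned to treatment sequentially, and asked to swallow the following", and the table that follows has six rows. Rows 1 and 2 carry three VHH-1 capsules each, rows 3 and 4 three VHH-2 capsules, and rows 5 and 6 three VHH-3 capsules. Every row also has one lysin capsule and the two transit-marker capsules.

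In cohort 2, according to the synopsis, "participants will receive 1 enteric capsule of each of the LMN-201 VHH proteins". Cohort 1 is therefore the only place where a subject takes one VHH without the other two.

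Two further passages bear on a short cohort. Section 5.4 says: "Each cohort will be considered completed when the total number of participants have completed their participation". Section 7.4 provides for replacement only before dosing: "Subjects who withdraw from the study prior to treatment will be replaced per recruitment and enrollment processes". No minimum size and no early-stop rule for cohort 1 is given.

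**The concern.** Sequential assignment down a table sorted by VHH places all the VHH-3 subjects last. Because the cohort size is a maximum, a cohort 1 that falls short loses subjects from the bottom of the table, so the loss falls on one component and is not spread over the three. That would leave a hole in the analysis cohort 1 exists to provide.

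The same ordering has a second effect that does not depend on a shortfall. VHH type runs nearly in step with enrolment order. If collection, filtering or handling of the fluid at the site changes as staff gain experience, that change lines up with the step from VHH-1 to VHH-2 to VHH-3.

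**Working it through.** **The plan's own figure.** Two cohorts of up to six give 2 × 6 = 12, which agrees with section 11.2: "Overall, up to 12 human subjects will be exposed to the IP". The protocol makes no sample size calculation, so no power formula applies.

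**Coverage.** Inputs: the cohort 1 table in section 5.1, read as the order 1, 1, 2, 2, 3, 3; the alternative order 1, 2, 3, 1, 2, 3; and cohort 1 ending after n subjects, n = 1 to 6. Subjects on VHH-1/VHH-2/VHH-3:

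| n | As written | Interleaved |
|---|---|---|
| 1 | 1/0/0 | 1/0/0 |
| 2 | 2/0/0 | 1/1/0 |
| 3 | 2/1/0 | 1/1/1 |
| 4 | 2/2/0 | 2/1/1 |
| 5 | 2/2/1 | 2/2/1 |
| 6 | 2/2/2 | 2/2/2 |

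All three VHHs are represented from subject 5 as written and from subject 3 interleaved. At no n does interleaving cover fewer VHHs. For VHH-3 the gain is confined to n = 3 and n = 4; at n = 2 there is a gain for VHH-2. The price at n = 3 and n = 4 is one fewer VHH with two subjects (none instead of one at n = 3; one instead of two at n = 4).

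**Alignment with enrolment order at n = 6.** The positions 1 to 6 have mean 3.5 and total sum of squares 2 × (2.5² + 1.5² + 0.5²) = 17.5. The between-VHH sum of squares is 2 × Σ(mean position of the VHH − 3.5)².

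- As written: mean positions 1.5, 3.5, 5.5. Sum of squares 2 × (4 + 0 + 4) = 16; share 16/17.5 = 91%.
- Interleaved: mean positions 2.5, 3.5, 4.5. Sum of squares 2 × (1 + 0 + 1) = 4; share 4/17.5 = 23%.
- Mirrored second block (1, 2, 3, 3, 2, 1): mean positions 3.5, 3.5, 3.5. Sum of squares 0; share 0%.

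**What a drift would do.** Assume, for illustration, that handling shifts the EIA result by b per enrolment position. The protocol gives no value for b and no evidence that it differs from zero. The difference VHH-3 minus VHH-1 is then biased by (5.5 − 1.5)b = 4b as written, (4.5 − 2.5)b = 2b interleaved, and 0 with the mirrored order.

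**The case against.** The strongest reply is that a short cohort 1 is hypothetical. The only planned reduction, from six to three, is for cohort 2, and it may be why the size is worded as a maximum. The cohort 1 table has six rows, withdrawals before dosing are replaced, and participation is one day with a witnessed dose, so there is little room for loss after dosing. This stands: the chance of ending at exactly three or four cannot be derived from the protocol. Still, a shorter cohort is not excluded, since no minimum is set.

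On drift, section 8.1 has aliquots treated with protease inhibitor, flash frozen and shipped at the end of the study, so a learning effect could enter only at site collection and processing. Spiked pre-dose fluid serves as a positive control, and every subject takes the same lysin capsule, which gives a common reference. No comparison between VHHs is planned, and with two subjects per VHH any difference is already mixed with differences between people. These points stand and limit the weight of the drift argument. They reduce the problem without giving a reason for the paired order.

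A reader might infer that any early stop leaves VHH-3 with no data at all. The protocol does not support that. At five subjects VHH-3 has one subject under either order. If cohort 2 runs, every subject in it takes a VHH-3 capsule, so what is lost is the single-VHH data only. Cohort 2 does not replace them: VHH-3 is given there at one capsule rather than three, alongside VHH-1 and VHH-2, and possibly in immediate release capsules if that adaptation is triggered.

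**Conclusion.** The point holds, at low severity. If cohort 1 ends at three or four subjects, the paired order leaves VHH-3 with no subject who took it without the other two VHHs, and an interleaved order would have given at least one. At one, two, five or six subjects the order makes no difference to VHH-3.

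At full enrolment the paired order also ties VHH type closely, though not completely, to enrolment position (91% against 23%). It would be too much to say that a drift exists or that interleaving would remove its effect: the protocol shows no drift, and the simple interleaved order halves a linear one.

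The consequences reach only the exploratory EIA data, which are descriptive, and cohort 1's stated purpose. The primary endpoint is visual and not specific to any VHH, and the adaptation rules use capsule counts and transit time. The conclusion assumes that subjects are dosed strictly in table order, as section 5.1 states, and that a shortfall removes subjects from the end of the table.

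**What to change.** Reorder the cohort 1 table in section 5.1 to VHH-1, VHH-2, VHH-3, VHH-1, VHH-2, VHH-3. Two alternatives give the same coverage from the third subject: mirror the second block (VHH-3, VHH-2, VHH-1), which also cancels a linear drift when all six enrol, or randomise the order within two blocks of three. Capsules per subject, visits and the 2/2/2 total do not change.

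The cost is a minor amendment, since section 5.1 requires ethics review and approval of changes it does not already describe. It needs no extra subjects or product. Any of these orders reduces the dependence on enrolment order; none makes a comparison of two subjects against two informative.

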4. OBJECTIVES AND ENDPOINTS

OBJECTIVES	ENDPOINTS
Primary	
To determine if enteric coating on components of LMN-201 is sufficient to deliver therapeutic proteins to the terminal ileum.	Presence or absence of capsules and/or transit markers in ileostomy fluid by visual observation

OBJECTIVES		ENDPOINTS	
Exploratory			
To document the presence of LMN-201 therapeutic proteins at the terminal ileum		Detect presence of LMN-201 therapeutic proteins (VHHs and lysin) in collected ileostomy fluid by EIA	
Exploratory			
To determine variability between individuals in the quantity of LMN-201 therapeutic proteins at the terminal ileum		Quantitate LMN-201 therapeutic proteins (VHHs and lysin) in collected ileostomy fluid by EIA	

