7.2 Study Visit

Subjects will be asked to refrain from eating after 11 p.m. the night before arrival at study facility. The following procedures will be performed upon arrival:

- Assessment of inclusion/exclusion criteria
- Record concomitant medications
- Vital signs including heart rate, respiratory rate, seated blood pressure, and temperature
- Physical exam
- Urine sample
- Collect ileostomy fluid
- Administer study product

After IP is administered, the following procedures will be conducted every hour until study staff observe capsules or transit markers in ileostomy fluid collection:

- Collect ileostomy fluid for analysis as described in MOP
- Monitor for AEs and measure vital signs

After any transit markers is observed in the ileostomy fluid, study staff will repeat ileostomy fluid collection procedures hourly for a minimum of 4 additional hours or 12 hours total study participation, whichever comes first.

Participants can start eating 2 hours after dosing.

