8. STUDY EVALUATIONS

8.1 Specimen Preparation, Handling, and Shipping

Ileostomy fluid is collected prior to the administration of study capsules, filtered, and aliquoted (either unadulterated or supplemented with purified proteins and protease inhibitor to use as a positive control). Once study capsules are administered, ileostomy content is collected hourly for the duration of the protocol (up to 12 hours). Upon collection, they are filtered, and the retained material is examined for the presence of intact capsules, capsule remnants, and transit markers. If these are observed, a photograph is taken to record the findings. The pH and volume of the filtrate are measured and recorded. Five 10 mL aliquots are prepared, supplemented with a protease inhibitor, and immediately flash frozen and stored at -80 °C until shipment. For shipment, one positive control, half of the pre-treatment samples, and 1 tube from each timepoint are assembled and transported on dry ice to Lumen Bioscience at the end of the study.

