9.2 Dosing Regimen

Subjects will receive individually encapsulated components of LMN-201, taken as four (4) capsules (500 mg biomass in each capsule), orally. In addition, they will receive an immediate release capsule containing ring-shaped transit markers and an enteric capsule containing tube-shaped transit markers to allow calculation of transit time and encapsulation dissolution visually.

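### Transit markers are scored only by presence and the stop is not tied to complete passage, so a low protein amount cannot be separated into digestion and incomplete passage; hourly marker counts would flag this cheaply

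*Protocol*

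**What the plan says.** Every section of the protocol that describes marker assessment describes it as presence.

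- The primary endpoint in Section 4 (and the Synopsis) is "Presence or absence of capsules and/or transit markers in ileostomy fluid by visual observation".
- Section 5.1 has hourly fluid "ileostomy fluid will be collected, weighed, filtered, and analyzed for the presence of capsules and/or transit markers".
- Section 8.1 says that, after filtration, "the retained material is examined for the presence of intact capsules, capsule remnants, and transit markers". If any are found, "a photograph is taken to record the findings". The filtrate's volume is also recorded.
- Section 9.2 gives the purpose of the two marker capsules: "to allow calculation of transit time and encapsulation dissolution visually". It mentions no recovered fraction, and the number of markers per capsule is not stated.

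On stopping, Section 5.1 says "This procedure will be repeated for four hours after the capsules and/or transit marker are observed in the ileostomy collection", or until 12 hours after ingestion if that is sooner. Section 7.2 starts the four further hours (there worded as a minimum) "After any transit markers is observed in the ileostomy fluid". The immediate release marker can therefore start the clock.

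On protein, an exploratory endpoint in Section 4 is "Quantitate LMN-201 therapeutic proteins (VHHs and lysin) in collected ileostomy fluid by EIA". It is tied to an objective on variability between individuals. Section 5.1 adds that the first cohort uses separate components so that the digestion of each can be examined, with two subjects per VHH.

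**The concern.** The protein recovered by the stop depends on two things: how much of the capsule contents had reached the stoma, and how much of the protein in those contents had survived. The plan measures the combined result by EIA but plans no measure of the first part. The stop comes at a subject-specific time, from 5 hours (first sighting at hour 1, plus 4) to 12 hours after dosing.

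A subject with slow enteric passage and intact protein can then look the same as one with complete passage and heavy digestion. Differences in passage between subjects can also look like differences in protein survival. With two subjects per VHH in the first cohort, one truncated collection could change the reading for that component. No later analysis can use counts that were never recorded.

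**Working it through.** The protocol gives no figure for marker recovery or share passed, so there is none to reproduce. The number of markers per capsule, M, is an assumption, shown at 10, 20 and 24. The 25% protein recovery below is also only an illustration.

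**Step 1. What a presence score reveals.** Let F be the share of the enteric contents passed by the stop. If markers move independently, P(at least one seen) = 1 − (1 − F)^M. For M = 20 and F = 0.25 this is 1 − 0.75^20 = 0.997.

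| F | M = 10 | M = 20 | M = 24 |
|---|---|---|---|
| 0.10 | 0.65 | 0.88 | 0.92 |
| 0.25 | 0.94 | 0.997 | 0.999 |
| 0.50 | 0.999 | about 1 | about 1 |
| 1.00 | 1 | 1 | 1 |

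A sighting therefore does not distinguish a quarter passed from all passed.

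**Step 2. What this does to the protein amount.** Let R be the protein recovered as a fraction of dose and S the fraction surviving digestion. Then R = F × S, so S = R / F. With R = 0.25, F = 1 gives S = 0.25 (75% digested), and F = 0.25 gives S = 1 (none digested). Presence alone leaves S anywhere from 25% to 100%, a fourfold range.

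**Step 3. What a count would add.** The table gives the Clopper-Pearson 95% interval for F from the count recovered, then S = 0.25 / F, capped at 1.

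| Recovered / loaded | F | S |
|---|---|---|
| 20/20 | 0.83–1.00 | 25–30% |
| 18/20 | 0.68–0.99 | 25–37% |
| 10/20 | 0.27–0.73 | 34–92% |
| 6/20 | 0.12–0.54 | 46–100% |
| 10/10 | 0.69–1.00 | 25–36% |
| 5/10 | 0.19–0.81 | 31–100% |
| 24/24 | 0.86–1.00 | 25–29% |
| 12/24 | 0.29–0.71 | 35–86% |

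The count is informative when recovery is near complete. At about half or less it mainly shows that the collection was cut short. These intervals treat markers as independent and as moving with the protein, so they are optimistic.

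**Step 4. How good one marker capsule is as a proxy.** A simulation compared the share passed from one enteric marker capsule with that from three VHH capsules. All transit inputs were assumed:

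- first immediate release marker at mean 3.5 h (SD 1 h), rounded up to the next hourly collection, then four more hours, capped at 12 h;
- enteric contents at mean 6 h (SD 1 h between subjects), with a spread of 1.5 h within a capsule.

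The root mean square error in F was 0.09, 0.17 and 0.29 for a between-capsule SD of 0.5, 1 and 2 h. The proxy is useful if capsules travel together and weak if they do not.

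**Step 5. Which marker is the enteric one.** The Synopsis puts the ring-shaped markers in the enteric capsule and the tube-shaped ones in the immediate release capsule. Sections 9.1 and 9.2 state the reverse. Until these are reconciled, a count by shape cannot be assigned to the right capsule type.

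**The case against.** The strongest reply is that the protocol is not silent on passage. Each hourly collection is examined, so first and last appearance are available, by shape if so recorded. Findings are photographed, so a later count may be possible. The 20% adaptation rule in Section 5.1 already needs a number of capsules still encapsulated. Collection details are left to a Manual of Procedures that is not shown, and a count there cannot be excluded. A reader might infer that the share passed is wholly unknown; the documents do not support that. What stands is that no section plans a count, from photographs or otherwise, and that the endpoint itself is worded as presence.

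Second, the markers have another stated purpose, and no endpoint is a survival fraction. The variability objective concerns an amount, which can be reported without a denominator. This is fair, and the primary endpoint is not invalidated. But Section 5.1 does intend a reading on digestion, and that reading does need to know what had passed.

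Third, a reader might infer that counting repairs the protein total. It does not. The stopping rule is unchanged, one marker capsule stands in for four drug capsules, and markers from one capsule share its dissolution and transit. If they arrive together, the binomial intervals are too narrow. Nor does full marker recovery prove digestion, since intact capsules or biomass held on the filter could also lower measured protein.

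**Conclusion.** The point holds as a cheap improvement to exploratory endpoints. Presence-only scoring, combined with a stop not tied to complete passage, leaves a low protein amount in the first cohort open to two explanations that the planned data only partly separate. In the illustration (25% of dose recovered), survival could be 25% to 100%. A full count of an assumed 20 markers would narrow this to 25–30%, whereas a half count would leave 34–92% and serve mainly as a warning.

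These sizes rest on the assumed marker number, the assumed protein recovery, independent markers, and markers moving with the protein. None of these is given in the protocol. The direction does not depend on the exact number: at M = 10 the chance of a sighting is already 0.94 with a quarter passed.

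**What to change.** 1. Reconcile the Synopsis with Sections 9.1 and 9.2 on which marker shape is in the enteric capsule.
2. In Sections 4, 5.1 and 8.1, keep the presence endpoint and add a count of each marker shape in every hourly collection. Record the number loaded per capsule. If the Manual of Procedures already requires a count, state it in the protocol.
3. Report cumulative marker recovery (recovered / loaded) by capsule type at the stop, with enteric-marker recovery beside each subject's EIA amount. If the second cohort's drug capsules become immediate release under the Section 5.1 adaptation, the matching marker is the one in the immediate release capsule.
4. Describe a low protein amount as consistent with digestion only where matching-marker recovery is near complete and no intact drug capsules were retained. Otherwise report it as a possibly truncated collection.

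The cost is two count fields per collection, one record of the number loaded, and a few minutes per collection. No dose, visit or sample changes. The recovery figure should be labelled an approximate guide, not used as a divisor to correct the protein amount.

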1.2 Schedule of Activities (SoA)

	Screening Visit	Study Visit		End of Study
		Dose	Follow up	
	Day -15 to 0	Hour 0	Hourly for 4 hours following observation of any transit markers or capsules, or for 12 hours, whichever time is shorter	
Study Procedures				
Consent	X			
Inclusion/exclusion criteria	X	X		
Medical History	X			
Physical Exam	X	X		
Vitals signs	X	X	X	
Urine Sample	X	X		
Study investigational product (IP) administered		X		
Collect ileostomy fluid for analysis ¹		X	X	
Record AEs			X	
Ship ileostomy fluid ¹				X

¹ See Manual of Procedures (MOP) for complete descriptions.

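### The 4-hour collection clock can be started by the immediate-release marker alone, so required collection can end before later enteric items arrive; the 12-hour cap and the 4-hour wording also differ between sections

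*Protocol*

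**What the plan says.** Four sections of the Protocol set the collection rule.

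- **Section 1.1 (Synopsis):** "The procedure will be repeated for 4 hours after capsules and/or transit markers are observed in the collected ileostomy fluid, or 12 hours after ingestion". The shorter of the two applies.
- **Section 1.2 (Schedule of Activities):** "Hourly for 4 hours following observation of any transit markers or capsules, or for 12 hours, whichever time is shorter".
- **Section 5.1 (General Study Design):** "This procedure will be repeated for four hours after the capsules and/or transit marker are observed in the ileostomy collection, or 12 hours after ingestion". Again the shorter of the two applies.
- **Section 7.2 (Study Visit):** after dosing, "the following procedures will be conducted every hour until study staff observe capsules or transit markers in ileostomy fluid collection". A second phase follows: "After any transit markers is observed in the ileostomy fluid, study staff will repeat ileostomy fluid collection procedures". Its length is given as: "hourly for a minimum of 4 additional hours or 12 hours total study participation, whichever comes first".

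Section 9.2 says that each subject also receives "an immediate release capsule containing ring-shaped transit markers and an enteric capsule containing tube-shaped transit markers to allow calculation of transit time". The same sentence gives a second purpose, judging by eye how the capsules dissolve. The Synopsis assigns the shapes the other way round: "1 enteric capsule containing ring-shaped transit markers, and 1 immediate release capsule containing tube-shaped transit markers". Section 9.1 agrees with 9.2.

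Section 5.2 estimates that all of a participant's study visits together take no more than 12 hours. Section 8.1 allows hourly collection for up to 12 hours once the capsules have been given. Sections 1.2 and 7.2 refer to the Manual of Procedures (MOP) for the details of collection.

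**The concern.** The study asks whether enteric capsules deliver protein to the terminal ileum. Two marker capsules with different release behaviour are useful because their contents may appear at different times. The stopping rule does not use that distinction: any marker or capsule, including the immediate-release marker, starts the 4 hours. No section says that a later sighting restarts them.

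Two uses of the data are exposed.

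- **Cohort 2 adaptation (section 5.1).** The first rule depends on intact enteric capsules being observed in more than one participant, and then on whether transit time is below or above 4 hours. An intact capsule that arrives after collection has ended is not observed and cannot count.
- **EIA results (section 4).** Protein that arrives after collection has ended is missing from the measured quantities.

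Separately, staff cannot follow all the stated caps and durations at once.

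**Working it through.** The protocol makes no sample-size or power calculation (section 11.2), so there is no stated figure to reproduce. The check covers the stopping rule itself and the wording side by side.

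**1. When required collection ends.** Let t be the hour after ingestion at which the first capsule or marker of either type is seen. With the 4-hour tail and the 12-hour cap of sections 1.1 and 5.1:

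close = min(t + 4, 12); unsampled hours = 12 − close

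| t | close | unsampled |
|---|---|---|
| 1 | 5 | 7 |
| 2 | 6 | 6 |
| 3 | 7 | 5 |
| 4 | 8 | 4 |
| 5 | 9 | 3 |
| 6 | 10 | 2 |
| 7 | 11 | 1 |
| 8 or later | 12 | 0 |

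**2. When an enteric item is lost.** Suppose the immediate-release marker is first seen at hour t and an enteric item follows L hours later. The item is lost to early closure, rather than to the cap, when L > 4 and t + L ≤ 12. The protocol gives no value for L, so these are illustrations only:

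- t = 2, L = 4: arrives at hour 6, collection ends at hour 6, collected.
- t = 2, L = 5: arrives at hour 7, collection ended at hour 6, lost.
- t = 6, L = 5: arrives at hour 11, collection ended at hour 10, lost.
- t = 8, L = 5: arrives at hour 13, beyond the cap in any case.

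**3. The wording compared.**

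| Section | Trigger | Tail | 12-hour limit |
|---|---|---|---|
| 1.1 | capsules and/or markers | 4 h | from ingestion |
| 1.2 | any marker or capsule | 4 h | origin not stated |
| 5.1 | capsules and/or marker | 4 h | from ingestion |
| 5.2 | none | none | estimate for all study visits |
| 7.2 | capsules or markers end the first phase; only markers start the tail | at least 4 h | total study participation |

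Section 7.2 lists eligibility checks, vital signs, physical examination, urine and baseline fluid before dosing. If those take p hours and participation is counted from arrival, its cap leaves 12 − p hours after dosing. For assumed p = 0.5, 1 or 2 that is 11.5, 11 or 10 hours. The protocol does not give p.

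The section 5.2 estimate cannot hold for a subject collected to 12 hours after ingestion. The Synopsis puts the screening visit at 1 to 2 hours, so 12 + 1 = 13 to 12 + 2 = 14 hours, before any pre-dose procedures.

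**The case against.** The strongest reply is that the loss is hypothetical. All six capsules are swallowed together, the enteric ones are designed to open at or before the terminal ileum, and the 4-hour tail is itself an allowance for later items. The table restates the rule and does not measure lost data. This stands: a reader might infer that the trial will lose enteric data, or some share of it, and the protocol supports neither, because it gives no lag.

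Second, section 7.2 sets a minimum of 4 hours, so staff may continue. This stands in part. It permits longer collection but does not require it, and sections 1.1, 1.2 and 5.1 take the shorter time.

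Third, the MOP may name the trigger. It might, but it cannot remove conflicts within the protocol.

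Two stronger readings are tempting and do not hold.

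- **Primary endpoint.** A reader might infer that early closure distorts it. That endpoint pools all capsules and markers. Closure before hour 12 happens only after one of them has been seen, so the result is already present. Whether pooling suits the objective is a separate question.
- **Variability between individuals.** A reader might infer bias because collection can run from 5 to 12 hours. Unequal length follows from tying collection to each subject's own transit, and nothing in the protocol shows that it biases this exploratory objective.

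**Conclusion.** The point holds in a limited form and should be fixed. As written in sections 1.1, 1.2 and 5.1, an immediate-release marker first seen at hours 1 to 7 ends required collection at hours 5 to 11. Enteric items arriving more than 4 hours after it, but within the 12 hours, then go uncollected. The consequences are confined to the adaptation rule that counts observed intact enteric capsules and to the EIA quantities.

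This assumes that the clock runs from the first sighting, which the 7.2 wording supports and no section contradicts, and that staff stop when they are allowed to. The frequency is unknown, and no percentage can be given. Confidence is medium for that reason and because the MOP is not shown.

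The conflicts over the cap, the tail and the trigger depend on no assumption about lag.

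**What to change.** In sections 1.1, 1.2, 5.1 and 7.2, state that an immediate-release marker alone does not start the 4-hour clock, and adopt one of two rules.

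- **Collect every subject hourly to the 12-hour cap.** This is the simplest and needs no trigger.
- **Start the clock at the first enteric item and restart it at each later one, up to the cap.** Without the restart, the first of five enteric capsules could close collection on the other four. This option first needs three things:
  - the ring and tube assignment reconciled (1.1 against 9.1 and 9.2);
  - a list of qualifying items that staff can recognise by eye, since the protocol does not say that remnants of the two capsule types can be told apart;
  - a stated trigger for a second cohort switched to immediate-release capsules.

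Under either rule, reconcile the cap and the 4-hour wording across 1.1, 1.2, 5.1, 5.2 and 7.2, and match the MOP. Section 5.2 matters most under the first rule, which would bring every subject into conflict with its estimate if the cap runs from ingestion.

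**Cost.** Amendment wording, longer stays for some subjects, and at most 7 more hourly collections each, if every subject would otherwise have closed at hour 5. That is 7 × 12 = 84 collections, or 7 × 9 = 63 if the second cohort is reduced to three. At the five aliquots per collection in section 8.1, the upper bounds are 84 × 5 = 420 and 63 × 5 = 315 aliquots. All fall within the up to 12 hours of post-dose collection that section 8.1 already allows.
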